5.4.3.2 Circulating Tumor Cell Analysis

Descriptive statistics will be used to evaluate CTC count at each timepoint. CTC changes from baseline will be plotted and summarized at each timepoint.

The number and proportion of participants who have a baseline CTC value ≥ 1 cell/7.5 mL and who subsequently have at least one post-baseline CTC value equal to zero (i.e. CTC0) will be presented within each cohort. 95% CIs for the proportion of CTC0 participants will be estimated using the Clopper-Pearson method. Participants with a missing baseline CTC value or baseline CTC value < 1 cell/7.5 mL will be excluded from the CTC0 analysis.

5.4.3.3 Prostate-specific Antigen Analysis

Descriptive statistics will be used to evaluate PSA at each timepoint. The percent change from baseline will be plotted and summarized at each timepoint. The maximum percent change (decrease) in PSA at any point after initiation of study invention will be summarized and displayed in a waterfall plot. The analysis of percent change in PSA from baseline at 12 weeks will use the first PSA value that is collected at least 12 weeks (\pm visit windows specified in the cohort-specific protocol appendix) after the initiation of study intervention.

Time to PSA progression is defined as the time from initiation of study invention to the date that a $\geq 25\%$ increase and absolute increase of ≥ 2 ng/mL above the nadir (or baseline value

for participants who did not have a decrease) in PSA. The increase must be confirmed by a second consecutive PSA assessment conducted at least 3 weeks later. If confirmed, the date that the PSA criteria were first met will be considered the date of PSA progression. Participants who do not progress will be censored at the last available PSA measurement prior to the initiation of subsequent anti-cancer therapy. Time to PSA progression will be estimated using Kaplan-Meier techniques, and the median progression time and 95% CIs will be estimated within each cohort. If median progression time is not reached, progression times and 95% CIs will be reported at deciles that are estimable given the observed events.

5.4.3.4 Duration of Response

For participants who have measurable disease at baseline and who experienced an objective response (confirmed CR or PR) during the study, DOR is defined as the time from the first tumor assessment that documents response (CR or PR, whichever is recorded first) to the first documentation of radiographic PD per PCWG3-modified RECIST v1.1 or death due to any cause (whichever occurs first).

Participants who have not progressed at the time of analysis will be censored as follows:

- Participants who do not have radiographic PD and are still on study at the time of analysis will be censored at the date of the last tumor assessment documenting response
- Participants who have discontinued study treatment and have started subsequent anti-cancer therapy or had subsequent cancer surgery or radiation prior to documentation of radiographic PD will be censored at the date of the last tumor assessment documenting response that occurred prior to the initiation of subsequent systemic treatment.
- Participants who discontinued the study prior to documentation of radiographic PD will be censored at the date of the last tumor assessment documenting response.

DOR will be estimated using Kaplan-Meier techniques, and the median DOR and 95% CIs will be estimated within each cohort. If median DOR is not reached, duration times and 95% CIs will be reported at deciles that are estimable given the observed events.

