Appendix Table 1: Response Based on Evaluation of Target Lesions at Each Assessment

Complete response	Disappearance of all target lesions; if a pathologic lymph node, reduction in the shortest axis to < 10 mm ^a
Partial response ^b	$\geq 30\%$ decrease in the sum of the diameters of target lesions relative to the baseline sum diameters ^c
Stable disease ^{b,d}	Neither a sufficient reduction to qualify as a partial response nor a sufficient increase to qualify as progression ^c
Progressive disease ^b	$\geq 20\%$ increase in the sum diameters relative to the smallest sum diameters recorded (including the baseline sum diameters) in conjunction with an increase of at least 5 mm in that smallest sum diameters, or the appearance of 1 or more new lesions ^{c,e}

^a For each pathologic lymph node considered a target lesion, the node must have a short axis measuring < 10 mm to be considered as a complete response. In such cases, the sum diameters may not be zero (as a normal lymph node can have a short axis of < 10 mm).

^b For each pathologic lymph node considered a target lesion, the measurement of the short axis of the node is to be included in the sum diameters when determining partial response, stable disease, and progression.

^c In this study, the “baseline sum diameters” is calculated based on the lesion measurements obtained at screening.

^d Duration of stable disease is measured from the date of the first dose of Study treatment until criteria for progressive disease are met based on the smallest sum diameters recorded (including the baseline sum diameters).

^e The finding of a new lesion should be unequivocal and not possibly attributable to a difference in imaging modality or scanning technique. Post-baseline, fluorodeoxyglucose positron emission tomography (FDG-PET) may be useful in assessing new lesions apparent on CT scan.

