5.4.2.3 Radiographic Progression-Free Survival

rPFS is defined as the time from initiation of study intervention to the first objective evidence of radiographic progression or death due to any cause (whichever occurs first). Radiographic disease progression is defined as soft tissue (non-bone) disease progression per RECIST v1.1 or confirmed progression of bone disease per PCWG3 criteria. Participants who continue treatment beyond initial disease progression will be considered to have progression of disease (PD) at the time of the initial progression event.

Participants who do not have radiographic PD at the time of analysis will be censored as follows:

- Participants who do not have radiographic PD and are still on study at the time of analysis will be censored at the date of the last tumor assessment documenting absence of progressive disease
- Participants who have discontinued study treatment and have started subsequent anti-cancer therapy or had subsequent cancer surgery or radiation prior to documentation of radiographic PD will be censored at the date of the last evaluable tumor assessment prior to the initiation of subsequent treatment.
- Participants who discontinued the study prior to documentation of radiographic PD will be censored at the date of the last tumor assessment documenting absence of progressive disease.
- Participants who do not have radiographic PD and who die more than 16 weeks from their last evaluable tumor assessment will be censored at the date of the last tumor assessment documenting absence of progressive disease. Participants who within 16 weeks of their last evaluable tumor assessment will be considered as having an event at the date of death.

rPFS will be estimated using Kaplan-Meier techniques, and the median survival time and 95% CIs will be estimated within each cohort. If median survival is not reached, survival times and 95% CIs will be reported at deciles that are estimable given the observed events.

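### Duration of response is censored at the last scan still in CR or PR, not the last scan without progression, so event-free time is dropped and the curve is biased downward

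*SAP*

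**What the plan says.** SAP 5.4.3.4 starts DOR at the first scan showing CR or PR and ends it at radiographic PD or death from any cause. Three bullets cover responders who have not progressed:

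- Still on study (bullet 1) or left the study before PD (bullet 3): "censored at the date of the last tumor assessment documenting response".
- New anti-cancer therapy, surgery or radiation before PD (bullet 2): the last scan "documenting response that occurred prior to the initiation of subsequent systemic treatment".

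The same section glosses a scan that documents response as one showing CR or PR.

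SAP 5.4.2.3 (rPFS) also ends at radiographic PD or death. Its bullets for participants still on study or off study say "will be censored at the date of the last tumor assessment documenting absence of progressive disease". Its new-treatment bullet uses the last evaluable scan before that treatment. A fourth bullet says that participants without PD "who die more than 16 weeks from their last evaluable tumor assessment will be censored" at the last scan without PD. DOR has no such bullet.

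Protocol Appendix Table 1 requires a fall of at least 30% from the baseline sum for PR. For target-lesion PD it requires a rise of at least 20%, and of at least 5 mm, from the smallest sum. Stable disease (SD) is what remains: "Neither a sufficient reduction to qualify as a partial response nor a sufficient increase to qualify as progression".

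SAP Section 6 records that DOR was added as an exploratory endpoint. It gives no reason for a censoring date that differs from that of rPFS.

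**The concern.** A responder stays at risk of the DOR event until PD or death. A later SD scan is an evaluable observation that the event has not happened. Under the DOR bullets the use of that scan depends on what comes afterwards: if PD follows, the whole interval counts; if PD has not occurred by the cut-off, the clock goes back to the last CR or PR scan. Censoring that depends on later event status is what Kaplan-Meier estimation must avoid, and here only event-free time is removed.

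Censored responders are likely, because SAP 3.4 allows the primary analysis once every participant has 6 months of follow-up or has left the study. What is at stake is the accuracy of the DOR curve, of individual durations, and of the deciles that the SAP reports when the median is not reached.

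**Working it through.** The plan states no figure for DOR, so there is none to reproduce. The error rates in SAP 3.3 concern the composite response rate and do not enter here.

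**1. Can a responder's later scan be neither response nor PD?** Let B be the baseline sum and N the nadir, in mm (Protocol Appendix Table 1).

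- PR holds while the sum is at most 0.70 × B.
- Target-lesion PD needs a sum of at least the larger of 1.2 × N and N + 5.
- The 20% condition governs when 1.2 × N ≥ N + 5, that is, N ≥ 25 mm. A gap then exists when N > 0.70 × B / 1.2 = 0.583 × B, a best shrinkage of 30% to about 41.7%.
- Below 25 mm the 5 mm condition governs, and a gap exists when N > 0.70 × B − 5, which is wider in relative terms.

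| B | N | N/B | PR up to | PD from | Gap |
|---|---|---|---|---|---|
| 100 | 70 | 70% | 70 | 84 | 14 |
| 100 | 65 | 65% | 70 | 78 | 8 |
| 100 | 60 | 60% | 70 | 72 | 2 |
| 100 | 55 | 55% | 70 | 66 | none |
| 30 | 16.5 | 55% | 21 | 21.5 | 0.5 |
| 20 | 10 | 50% | 14 | 15 | 1 |

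So the gap exists, mainly for shallow responses and small tumor sums.

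**2. One participant.** Scans follow the Protocol 1.3 schedule (every 8 to 9 weeks to week 24, then every 12). Suppose PR at weeks 8 and 16 and SD at weeks 24 and 36.

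- No PD at cut-off, SAP rule: 16 − 8 = 8 weeks, censored.
- No PD at cut-off, last scan without PD: 36 − 8 = 28 weeks, censored.
- PD at the next scan, week 48: 48 − 8 = 40 weeks, an event. The SD time now counts in full.

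**3. Direction.** Earlier censoring leaves the events unchanged and can only shrink the risk set at each event time. Each factor 1 − d/n is therefore the same or lower, and so is the curve.

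Assumed example, six responders, weeks from first response: PD at 16, 28 and 40. The other three have last response scans at 16, 40 and 8, and last scans without PD at 40, 40 and 16.

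| | SAP rule | Last scan without PD |
|---|---|---|
| Week 16 | 4/5 = 0.800 | 5/6 = 0.833 |
| Week 28 | 0.800 × 2/3 = 0.533 | 0.833 × 3/4 = 0.625 |
| Week 40 | 0.533 × 1/2 = 0.267 | 0.625 × 2/3 = 0.417 |
| Median | 40 | 40 |
| Person-weeks | 148 | 180 |

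The loss is 32/180 = 18% of person-time.

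**4. Size over a range.** The documents do not say how often SD follows response. A simulation assumed exponential DOR with median 36 weeks, cut-off uniform between 13 and 60 weeks after response, and one SD scan dropped in 10%, 25% or 50% of censored responders. The person-time lost was 2.4%, 6.1% or 12.1%. The estimated median was 40 weeks throughout; PD dates fall on scan dates, so the median moves only in steps.

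**5. Late deaths.** Take a responder last scanned at week 28, without PD, who dies at week 48. The interval is 20 weeks, which exceeds 16. DOR records an event at week 48. The rPFS rule would censor at week 28. Here DOR keeps the time and rPFS drops it.

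**The case against.** The best defense is that the wording is deliberate. It appears in all three bullets, and one could want DOR to credit only time with response on the scan. But DOR does not end when response is lost without PD, and SD time is credited in full to anyone who later progresses. A rule meant to credit only time in response would have to treat both groups alike.

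A second defense reads the phrase as response not yet lost to PD, in which case nothing is lost. That is possible but strained: the section glosses response as CR or PR, and the SAP uses a different phrase for absence of PD one endpoint earlier.

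The argument on size largely stands. New lesions, non-target growth and bone progression also end DOR, so fewer responders will sit in the gap than target-lesion arithmetic suggests. A 25% composite rate in 30 participants gives 7.5 responders, and DOR uses only those with measurable disease and a confirmed CR or PR. The cohort expansion rule uses the composite response rate, not DOR.

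A reader might infer that the missing late-death rule also discards DOR time. It does the reverse, as step 5 shows. The divergence is also narrow: with scans no more than about 12 weeks apart, the participant must miss a scheduled scan, have no PD, start no new treatment, remain on study and then die. Importing the 16-week rule into DOR would itself remove observed time.

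**Conclusion.** The concern holds for the censoring date. SAP 5.4.3.4 removes observed event-free time from censored responders whose later scans are SD, keeps the same kind of time for those who progress, and so biases the DOR curve downward. This rests on reading a scan that documents response as one showing CR or PR, as the section itself does.

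The effect is small. It is limited to censored responders with at least one later SD scan, each dropped scan costing roughly 8 to 12 weeks. The median will seldom change; individual durations, curve heights and deciles in a small cohort can. The 18% and the 2.4% to 12.1% rest on assumed data and illustrate scale only. DOR is exploratory, and no expansion decision, error rate, power or sample size depends on it.

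The late-death difference between DOR and rPFS is a separate inconsistency without a stated reason. The documents do not support treating it as a second source of lost DOR time.

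**What to change.** - **Bullets 1 and 3 of SAP 5.4.3.4:** adopt the rPFS date, "censored at the date of the last tumor assessment documenting absence of progressive disease", and specify that the assessment must be evaluable.
- **Bullet 2:** use the last such assessment before the start of any subsequent anti-cancer therapy, surgery or radiation. This also removes a mismatch: the bullet is triggered by surgery or radiation, but its cut-off refers only to systemic treatment.
- **Deaths:** state one rule for deaths long after the last evaluable scan in both DOR and rPFS, or give the reason for the difference. Say explicitly that a death without PD is not censored merely because it ends participation. Protocol 7.2 lists death among the reasons for leaving follow-up, so bullet 3 could be misread that way.

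The cost is SAP wording and the matching DOR derivation. No new data, visits or participants are needed.

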Radiographic disease assessment	X	Per PCWG3 guidelines: Every 8 to 9 weeks (± 1 week) for first 24 weeks, and every 12 weeks (± 1 week) thereafter until radiographic PD or start of subsequent therapy. Refer to the cohort appendix for each respective combination for cohort-specific details							
Review of alternate anticancer therapy ^o								X	X
Follow-up for overall survival								X	X

ADA = anti-drug antibodies; AE(s) = adverse event(s); AESI(s) = adverse event(s) of special interest; cfDNA = cell-free deoxyribonucleic acid; ECG = electrocardiogram; ECOG = Eastern Cooperative Oncology Group; EOT = end of treatment; I/E = inclusion/exclusion; PCWG3 = Prostate Cancer Clinical Trials Working Group 3; PD = progressive disease; PD-1 = programmed cell death 1; PK = pharmacokinetics; Q3M = every 3 months; SAE(s) = serious adverse event(s)

^a Tests/procedures performed as standard of care prior to obtaining informed consent and within 28 days prior to the first day of study intervention administration do not have to be repeated at screening.

^b The End of Treatment Visit will be completed following the last dose of study intervention, either at completion of the on-treatment phase or at early discontinuation.

^c For up to 2.5 years from the initiation of study intervention, participants in the follow up phase will be contacted by the site to collect alternate anticancer therapy information and determine survival status.

^d Informed consent must be obtained prior to any study-specific procedures and may be obtained prior to the 28-day screening window.

^e Body weight may be required more frequently for study interventions using weight-based dosing. Combination-specific frequency will be provided in the cohort appendix for each respective combination.

^f Blood samples should be collected prior to administration of any study intervention.

^g 12-Lead ECG will be collected at screening, Cycle 2 and Cycle 4.

^h Circulating tumor cells will be collected at baseline (ie, Day 1 of Cycle 1 prior to study intervention administration), Day 1 of each cycle (prior to study intervention administration), and EOT.

ⁱ cfDNA (blood) will be collected at baseline (ie, screening visit prior to study intervention administration), Day 1 of Cycle 2 and Cycle 4, and EOT.

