5.4 Efficacy Analysis

The analyses for clinical activity will be performed on the evaluable population, consisting of all participants in a cohort who received at least 1 dose of any component of the combination study intervention. Some efficacy endpoints may be analyzed on a subset of the evaluable population, as summarized in Table 3.

This study is not intended or powered for hypothesis testing or comparison between cohorts. Due to the exploratory nature of this study, no control of type I error will be applied for any of the endpoints.

Table 3: Populations for Efficacy Analysis

Endpoint	Analysis Population
CRR	Evaluable population
CTC response (component of CRR)	Participants with a baseline CTC value ≥ 5 cells/7.5 mL of blood
PSA response (component of CRR)	Participants with a PSA value at baseline
ORR (component of CRR)	Participants with measurable disease at baseline per PCWG3-modified RECIST v1.1
DCR	Evaluable population
rPFS	Evaluable population
OS	Evaluable population
Change in CTC from baseline	Participants with a CTC value at baseline
CTC0	Participants with a baseline CTC value ≥ 1 cell/7.5 mL of blood
Percent change in PSA from baseline	Participants with a PSA value at baseline
Time to PSA progression	Participants with a PSA value at baseline
DOR	Participants with measurable disease at baseline per PCWG3-modified RECIST v1.1 and a best overall response of CR or PR

CR = complete response; CRR = composite response rate; CTC = circulating tumor cells; CTC0 = a measure of zero CTC; DCR = disease control rate; DOR = duration of response; ORR = objective response rate; OS = overall survival; PCWG3 = Prostate Cancer Clinical Trials Working Group 3; PR = partial response; PSA = prostate-specific antigen; RECIST = Response Evaluation Criteria in Solid Tumors; rPFS = radiographic progression-free survival

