6 DIFFERENCES COMPARED TO PROTOCOL

The following list provides a high-level overview of the differences between the SAP and the Core Protocol and cohort-specific appendices. The Core Protocol will be amended to address differences related to study endpoints.

- Section 3.2 (Study Objectives and Endpoints):
 - The SAP renames the Secondary composite endpoint from ORR to Composite Response Rate (CRR).
 - The SAP removes the requirement that at least 2 post-baseline PSA measurements must be available for a participant to be evaluable for the PSA response criterion of CRR.
 - The CRR criterion of confirmed response of CR or PR by objective radiographic disease assessment has been named ORR (objective response rate).
 - The SAP clarifies that participants without measurable disease at baseline will not be evaluable for ORR analysis.
 - The SAP modifies the minimum duration of SD required for a participant to be considered a DCR responder from 9 months to 6 months.
 - The SAP adds duration of response (DOR) as an exploratory endpoint.
- Section 3.3 (Determination of Sample Size): The SAP renames the Secondary composite endpoint from ORR to CRR.
- Section 5.1.1 (Evaluable Population): The SAP clarifies that some efficacy analyses may be performed on a subset of the evaluable population, as appropriate and detailed in other sections of the SAP.

- Section 5.4 (Efficacy Analysis): The SAP clarifies that some efficacy analyses may be performed on a subset of the evaluable population, as detailed in Table 3.
- Section 5.4.2.1 (Composite Response Rate):
 - The SAP renames the Secondary composite endpoint from ORR to Composite Response Rate (CRR).
 - The SAP clarifies that participants with a missing CTC value at baseline will not be evaluable for the CTC response criterion of CRR.
 - The SAP removes the requirement that at least 2 post-baseline PSA measurements must be available for a participant to be evaluable for the PSA response criterion of CRR.
 - The CRR criterion of confirmed response of CR or PR by objective radiographic disease assessment has been named ORR.
 - The SAP clarifies that participants without measurable disease at baseline will not be evaluable for ORR analysis.
 - The SAP clarifies that ORR responders must not have bone lesions that progressed, as determined by PCWG3 criteria.
 - The SAP clarifies that response rates and 95% CIs will be presented for each individual criterion of CRR.
- Section 5.4.2.2 (Disease Control Rate):

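### The duration-of-response censoring rule is triggered by surgery or radiation but takes its cut date only from systemic treatment, so the cut is inconsistent or undefined after local treatment

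*SAP*

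**What the plan says.** SAP 5.4.3.4 starts the clock at first documented response: "DOR is defined as the time from the first tumor assessment that documents response (CR or PR, whichever is recorded first"). It ends at radiographic progression or death. Table 3 in SAP 5.4 limits the analysis to "Participants with measurable disease at baseline per PCWG3-modified RECIST v1.1 and a best overall response of CR or PR".

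The second censoring bullet applies to participants who have discontinued study treatment and who "have started subsequent anti-cancer therapy or had subsequent cancer surgery or radiation prior to documentation of radiographic PD". It censors them at the "last tumor assessment documenting response that occurred prior to the initiation of subsequent systemic treatment".

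The matching rPFS bullet in SAP 5.4.2.3 has the same trigger, including discontinuation of study treatment, surgery and radiation. Its date rule is different: such participants "will be censored at the date of the last evaluable tumor assessment prior to the initiation of subsequent treatment". Nothing restricts that cut to systemic treatment.

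SAP section 6, which lists departures from the protocol, says only this about the endpoint: "The SAP adds duration of response (DOR) as an exploratory endpoint". It gives no reason for a narrower cut.

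**The concern.** Within one sentence the trigger and the date have different scopes. Someone put surgery and radiation into the trigger, presumably because a response seen after them can no longer be credited to the study combination alone. The date clause then ignores them.

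This matters because the response behind DOR is judged on soft-tissue lesions (SAP 5.4.2.1), which surgery or radiation can act on directly. Time in response after such treatment mixes the two effects. A programmer following the text would also have to decide, with the data in hand, what to do with a responder who had local treatment and no systemic therapy. With few responders per cohort, that one decision could be visible in the reported median.

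**Working it through.** **No stated figure to reproduce.** The documents give no number for DOR. Their only design calculation, the Simon two-stage design on the composite response rate in SAP 3.3, reproduces: type I error 0.0684 (stated 0.07), power 0.7745 (stated 77%) and early termination under the null 0.549 (stated 55%). None of it depends on the DOR rule. The check is therefore one of wording.

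**Step 1: trigger and cut compared.**

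| Endpoint | What brings the participant under the rule | What fixes the date |
|---|---|---|
| rPFS (SAP 5.4.2.3) | Treatment stopped, then anti-cancer therapy, surgery or radiation | Any subsequent treatment |
| DOR (SAP 5.4.3.4) | Same | Subsequent systemic treatment only |
| Time to PSA progression (SAP 5.4.3.3) | No progression | Subsequent anti-cancer therapy |

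Of the three, only DOR restricts the cut to systemic treatment.

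**Step 2: the rule applied to responders off study treatment and without progression.**

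- *Systemic therapy only.* The date is defined and matches the rPFS logic.
- *Local treatment, then systemic therapy.* The date is the last response scan before the systemic therapy. Response scans between the two treatments count.
- *Local treatment only.* There is no systemic start, so the bullet gives no date. The participant also fits the first bullet (still on study) or the third (left the study). Both use the last response scan with no cut at local treatment, so later scans may be counted. The text does not say which bullet governs.

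**Step 3: whether scans exist after local treatment.** The Schedule of Activities in protocol 1.3 images "every 12 weeks (± 1 week) thereafter until radiographic PD or start of subsequent therapy". Protocol 8.1 continues tumor assessments for participants who stop for reasons other than progression, and does not list subsequent therapy among the reasons to stop. If 1.3 governs and local treatment counts as subsequent therapy, few or no scheduled scans remain to be counted. If 8.1 governs, they continue.

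**Step 4: illustration on assumed data.** Take five responders. Four have events at 4, 6 and 8 months and one censoring at 10 months, measured from first response. The fifth, off study treatment, has radiation at month 4 (last earlier response scan at month 3), response scans to month 11 and systemic therapy at month 12.

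| Month | Systemic cut (fifth censored at 11) | rPFS-style cut (fifth censored at 3) |
|---|---|---|
| 4 | 4/5 = 0.80 | 3/4 = 0.75 |
| 6 | 0.80 × 3/4 = 0.60 | 0.75 × 2/3 = 0.50 |
| 8 | 0.60 × 2/3 = 0.40 | 0.50 × 1/2 = 0.25 |
| Kaplan-Meier median | 8 months | 6 months |

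The second median is 7 months if the software takes the midpoint when the estimate equals exactly 0.50.

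**Step 5: the direction is not fixed.** Suppose instead that the fifth responder progresses at month 5, after the radiation, and that this is counted as an event. The estimate at month 6 is then 4/5 × 3/4 × 2/3 = 0.40. Censoring at month 3 removes that event and gives 0.50, as in the table. Aligning the rules can therefore raise the curve as well as lower it.

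**The case against.** The strongest reply is that *systemic* is a stray word. Because the trigger lists surgery and radiation, a reasonable programmer would cut there anyway. That may well be the intention, but the SAP is the instruction to the programmer, and section 6 does not settle it.

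A second reply is that DOR and rPFS already differ by design: DOR censors at the last response scan, rPFS at the last progression-free scan, and only rPFS has the 16-week rule for deaths. This stands. Different censoring dates for one participant are not in themselves an error. The fault is the mismatch inside the DOR sentence; the rPFS bullet only shows how the same trigger is handled elsewhere.

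Third, the effect needs scans after local treatment, and protocol 1.3 may stop them. This also stands as a limit on size. It does not repair the rule, because protocol 8.1 reads differently and allows repeat scans when progression is suspected.

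A reader might infer more than the documents support:

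- *That time after local treatment is definitely credited to the combination.* This follows only when systemic therapy comes later and response scans fall in between. With local treatment alone the date is undefined.
- *That any irradiated responder is affected.* Both bullets require study treatment to have been discontinued. Palliative radiotherapy during treatment, which protocol 6.5.2 excepts from its prohibition, falls outside both and is a separate question.
- *That the number of responders can be worked out.* The 10% and 25% in SAP 3.3 are design rates for the composite response rate, not radiographic response. The minimum of 7 refers to a non-bone lesion that can be biopsied, not to measurable disease.

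**Conclusion.** The DOR censoring rule is wrong as written, and the matter is minor. For responders who have stopped study treatment, the rule counts response scans between local and later systemic treatment, and it has no defined cut after local treatment alone.

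The reach is narrow. DOR is exploratory and confined to radiographic responders with measurable disease. The composite response rate, the expansion rule, rPFS and overall survival do not use this rule.

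No size can be derived. The documents give no frequency of local treatment, no expected radiographic response rate and no number with measurable disease. The 8-versus-6-month example rests wholly on assumed data and on scans continuing after radiation. It shows only that one participant can move the median of a very small group.

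**What to change.** In SAP 5.4.3.4, second censoring bullet, replace the reference to subsequent systemic treatment with the first of subsequent anti-cancer therapy, cancer surgery or radiation, so that it matches 5.4.2.3. If a systemic-only cut is really intended, take surgery and radiation out of the trigger, state which bullet then covers those participants, and explain the departure from rPFS.

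Protocol 1.3 and 8.1 should also be reconciled on whether tumor assessments continue once subsequent therapy starts, since this decides how many scans the rule touches.

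The cost is a few words in the SAP and no new data. The downside is earlier censoring, and so less observed follow-up, in the few locally treated responders. Any progression after local treatment would no longer count as a DOR event.
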